9.2. Sample Size Determination

The study size is based on practical considerations in terms of feasibility of enrolling an adequate number of sites on each implementation strategy balanced with the desire to have interventions tested across several types of investigative sites; as well as enrolling an adequate number of patient study participants in each site.

Approximately 24 sites (from feasibility process) will be selected from the feasibility process to achieve 18 sites randomly assigned to study implementation strategies and approximately 54 evaluable staff study participants for an estimated total of 27 evaluable study staff participants per implementation strategy group.

Assuming 10% screen failures, it is estimated that with 18 sites approximately 527 patient study participants will be screened to achieve 474 subjects enrolled and 450 evaluable patient study participants completing the study (assumes 5% of patient study participants would be non-evaluable) for an estimated total of 225 evaluable patient study participants per implementation strategy group.

Power to Show Superiority in mean SSP AIM/IAM/FIM scores

Table 10 shows preliminary AIM/IAM/FIM data from the ongoing U.S. implementation study CUSTOMIZE (209493).

	N	Mean	SD	Median	Observed Range (min-max)	Floor n (%)	Ceiling n (%)	Skewness	Kurtosis
AIM Scale (Total Sample)	24	4.39	0.61	4.13	3.25-5.00	0 (0.0%)	11 (45.8%)	-0.16	-1.58
IAM Scale (Total Sample)	24	4.45	0.59	4.50	3.25-5.00	0 (0.0%)	12 (50.0%)	-0.34	-1.39
FIM Scale (Total Sample)	24	4.32	0.71	4.25	3.00-5.00	0 (0.0%)	11 (45.8%)	-0.47	-1.09

Table 10Staff Study Participants Scores at Month 4 in CUSTOMIZE (209493)

Based on these preliminary data from CUSTOMIZE study, and the given sample size (the number of study participants), the power to detect a difference of 0.5 between the implementation arms in terms of AIM, IAM and FIM are shown in Table 11.

Table 11 Power to Detect a 0.5 Difference in AIM/IAM/FIM

Endpoint	ARM-S	ARM-E	Delta	SD	Alpha	N(S)	N(E)	Power*
AIM	4.39	4.89	0.5	0.61	0.05	27	27	84%
						36	36	93%

Endpoint	ARM-S	ARM-E	Delta	SD	Alpha	N(S)	N(E)	Power*
IAM	4.45	4.95	0.5	0.59	0.05	27	27	86%
						36	36	94%
FIM	4.32	4.82	0.5	0.71	0.05	27	27	72%
						36	36	84%

*Power calculation using two-sided t-test assuming equal variance.

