As shown in Table 11, with 27 study staff participants (3 per site) surveyed on each arm, the study would have 72%-86% power to detect a 0.5 difference in FIM, AIM and IAM endpoints between ARM-E (Enhanced implementation strategy arm) and ARM-S (Standard implementation arm) assuming data from Table 10 (CUSTOMIZE study) for ARM-S.

And with 36 study staff participants (4 per site) surveyed on each arm, the study would have 84% - 94% power to detect a 0.5 difference in FIM, AIM and IAM endpoints between ARM-E and ARM-S.

Sample Size for Provider Population

An overall average number of 9 sites, per arm, would produces a two-sided 95% confidence interval with a distance from the mean paired difference (e.g. site level mean change from baseline in AIM, IAM or FIM score) to the limits (half-width) that is equal to 0.497 when the estimated standard deviation of the paired differences is 1.0, across sites.

Table 12Sensitivity Analysis for Sample Size versus Half-Width (Precision)-
Two-Sided 95% Confidence Interval (For Number of Sites)

[figure not shown]
Sample Size	Actual Distance from Mean		
	Difference to Lin	nits (Precision)	
	SD=0.5	SD=1.0	
10	0.358	0.715	
11	0.336	0.672	
12	0.318	0.635	
13	0.302	0.604	
14	0.289	0.577	
15	0.277	0.554	
16	0.266	0.533	
17	0.257	0.514	
18	0.249	0.497	
19	0.241	0.482	
20	0.234	0.468	

A sample size of 27 providers, per arm, produces a two-sided 95% confidence interval with a distance from the mean paired difference to the limits (half-width) that is equal to 0.396 when the estimated standard deviation of the paired differences is 1.0.

Table 13Sensitivity Analysis for Sample Size versus Half-Width (Precision)-
Two-Sided 95% Confidence Interval (for Number of Providers)

Sample Size	Actual Distance	from Mean
Campic Olze	Difference to Lin	
	SD=0.5	SD=1.0
21	0.228	0.455
22	0.222	0.443
23	0.216	0.432
24	0.211	0.422
25	0.206	0.413
26	0.202	0.404
27	0.198	0.396
28	0.194	0.388
29	0.190	0.380
30	0.187	0.373

[figure not shown]
Sample Size for Patient Population

A sample size of 225 patient subjects per implementation strategy group produces a twosided 95% confidence interval with a distance from the mean paired difference to the limits that is equal to 0.131 when the estimated standard deviation of the paired difference is 1.

Sample Size	Actual Distance Difference to Lin SD=0.5	
100	0.099	0.198
125	0.089	0.177
150	0.081	0.161
175	0.075	0.149
200	0.070	0.139
225	0.066	0.131
250	0.062	0.125

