2.4.1.2. Sample Size for Provider Population

An overall average number of 9 sites, per arm (18 sites), would produce a two-sided 95% confidence interval with a distance from the mean paired difference (e.g. site level mean change from baseline in AIM, IAM or FIM score) to the limits (half-width) that is equal to 0.497 when the estimated standard deviation of the paired differences is 1.0, across sites.

**Table C Sensitivity Analysis for Sample Size versus Half-Width (Precision)-
Two-Sided 95% Confidence Interval (For Number of Sites)**

Sample Size	Actual Distance from Mean Difference to Limits (Precision)	
	SD=0.5	SD=1.0
10	0.358	0.715
11	0.336	0.672
12	0.318	0.635
13	0.302	0.604
14	0.289	0.577
15	0.277	0.554
16	0.266	0.533
17	0.257	0.514
18	0.249	0.497
19	0.241	0.482
20	0.234	0.468

A sample size of 27 providers, per arm, produces a two-sided 95% confidence interval with a distance from the mean paired difference to the limits (half-width) that is equal to 0.396 when the estimated standard deviation of the paired differences is 1.0.

**Table D Sensitivity Analysis for Sample Size versus Half-Width (Precision)-
Two-Sided 95% Confidence Interval (for Number of Providers)**

Sample Size	Actual Distance from Mean Difference to Limits (Precision)	
	SD=0.5	SD=1.0
21	0.228	0.455
22	0.222	0.443
23	0.216	0.432
24	0.211	0.422
25	0.206	0.413
26	0.202	0.404
27	0.198	0.396
28	0.194	0.388
29	0.190	0.380
30	0.187	0.373

[figure not shown]

Figure A Sensitivity Analysis for Sample Size versus Half-Width (Precision)-Two-Sided 95% Confidence Interval (for Sites and Providers)

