2.4.1.3. Sample Size for Patient Population

A sample size of 225 patient subjects per implementation strategy group produces a two-sided 95% confidence interval with a distance from the mean paired difference to the limits that is equal to 0.131 when the estimated standard deviation of the paired difference is 1.

Table E Sensitivity Analysis for Sample Size versus Half-Width (Precision)-Two-Sided 95% Confidence Interval (for Patients)

Sample Size	Actual Distance from Mean Difference to Limits (Precision)	
	SD=0.5	SD=1.0
100	0.099	0.198
125	0.089	0.177
150	0.081	0.161
175	0.075	0.149
200	0.070	0.139
225	0.066	0.131
250	0.062	0.125

[figure not shown]
[figure not shown]

Figure B Sensitivity Analysis for Sample Size versus Half-Width (Mean Diff to Limit) versus Sample Size - Patients (Multiple Confidence Levels)

As explained in the protocol, launching CAB LA + RPV LA in the real world may present challenges that were not observed in a clinical trial setting. Therefore, in addition to the primary analyses which focuses on study staff participants data, statistical analyses of patient outcome endpoints will be performed to evaluate changes in study patients' satisfaction score results, to allow an informal comparison between the two implementation strategies.

CCI

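### The half-width of 0.497 given for 9 sites per arm is the value for all 18 sites pooled; 9 sites give 0.769

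*Protocol*

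**What the plan says.** Protocol section 9.2 gives three precision statements, each for a two-sided 95% confidence interval around a mean paired difference, that is, a mean change from baseline.

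- **Sites.** "An overall average number of 9 sites, per arm, would produces a two-sided 95% confidence interval with a distance from the mean paired difference". The half-width attached to this number of sites is 0.497 at SD 1.0. Table 12, whose title includes "Two-Sided 95% Confidence Interval (For Number of Sites", follows directly. It runs from n = 10 to n = 20 and lists 0.249 (SD 0.5) and 0.497 (SD 1.0) against n = 18.
- **Providers.** "A sample size of 27 providers, per arm, produces a two-sided 95% confidence interval"; its half-width is given as 0.396 at SD 1.0. Table 13 lists 0.396 against n = 27.
- **Patients.** 225 per implementation group give 0.131 at SD 1.0. Table 14 lists 0.131 against n = 225. SAP section 2.4.1.3 repeats the figure in a sentence that begins "A sample size of 225 patient subjects per implementation strategy group produces a".

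Earlier in section 9.2 the design is set "to achieve 18 sites randomly assigned to study implementation strategies", so 18 is the total over both arms. The SAP overview of the study design (section 2.3) gives 1:1 site randomization, hence 9 per arm.

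SAP section 2.4.1.2 rewords the site sentence: "An overall average number of 9 sites, per arm (18 sites), would produce a two-sided 95% confidence interval". It repeats 0.497, and its Table C is the same as Table 12, again starting at n = 10.

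**The concern.** The site sentence names 9 sites per arm but carries the half-width that its own table lists for 18. The tables have no row for 9, so the reader cannot look up the value that matches the label. The neighbouring provider and patient statements pair a per-arm label with a per-arm n, so a reader who follows the section's convention will take 0.497 as the precision within one arm.

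Sites are the unit of randomization (protocol section 6.3), and this is the only site-level precision figure in section 9.2; the power calculation in Table 11 counts individual staff. Protocol section 9.4.1 plans summaries of the AIM, IAM and FIM scores by implementation strategy, with 95% confidence intervals and change from baseline, so per-arm precision is a quantity a reader would want. What is at stake is whether that stated precision is one the design can deliver.

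**Working it through.** **Inputs**

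- Sites: 9 per arm in the sentence (protocol 9.2; SAP 2.4.1.2), 18 in total (protocol 9.2), randomized 1:1 (SAP 2.3).
- SD of the paired differences: 1.0 in the sentence; 0.5 is the other column of Table 12.
- Confidence level: two-sided 95%.
- Stated half-width: 0.497.

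**Formula.** For a one-sample (paired) mean, half-width = t(0.975, n − 1) × SD / √n.

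**Reproducing the plan's figure.** With n = 18 and SD 1.0: 2.110 × 1.0 / √18 = 2.110 / 4.243 = 0.497. The same formula reproduces every row of Table 12 (n = 10 to 20, both SD columns). The table is sound.

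**With the n named in the sentence.** With n = 9 and SD 1.0: 2.306 × 1.0 / √9 = 2.306 / 3 = 0.769. With SD 0.5: 0.384.

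| Sites | SD 0.5 | SD 1.0 |
|---|---|---|
| 9 (one arm) | 0.384 | 0.769 |
| 18 (both arms pooled) | 0.249 | 0.497 |

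**Size of the gap.** 0.7687 / 0.4973 = 1.546, so the 9-site interval is 1.55 times as wide. Equivalently, 1 − 0.4973 / 0.7687 = 0.353, so the stated half-width is 35% too narrow for one arm. SD cancels from this ratio, so it holds at any SD.

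**Could another method give 0.497 from 9 sites at SD 1.0?**

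| Variant, 9 sites per arm, SD 1.0 | Half-width |
|---|---|
| Normal quantile, two-sided 95% | 0.653 |
| t, one-sided 95% (same as a 90% interval) | 0.620 |
| Normal quantile, one-sided 95% | 0.548 |
| One arm, SD pooled over both arms (16 df) | 0.707 |
| Difference between arms, 9 versus 9 | 0.999 |

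None does. To obtain 0.497 from 9 sites, the SD would have to be about 0.65 (0.497 / 0.7687 = 0.647) or the confidence level about 83%. A between-arm difference at SD 0.5 gives 0.4997, which rounds to 0.500 and uses a different SD from the one stated.

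**Convention in the parallel statements (SD 1.0)**

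| Statement | Stated | Per-arm n | Pooled n |
|---|---|---|---|
| Providers, 27 per arm | 0.396 | 0.396 (n = 27) | 0.273 (n = 54) |
| Patients, 225 per group | 0.131 | 0.131 (n = 225) | 0.093 (n = 450) |
| Sites, 9 per arm | 0.497 | 0.769 (n = 9) | 0.497 (n = 18) |

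The provider and patient figures match the per-arm n. The site figure alone matches the pooled n.

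**The case against.** The best defence is that this is a slip of labelling and that a pooled interval was intended. The sentence opens by speaking of an overall number and ends with a reference to variation across sites; the table directly below lists 0.497 against 18; and the SAP names the 18 sites. A pooled interval would also have a use, because protocol section 9.4.1 plans overall summaries of the primary scores as well as summaries by arm. On that reading 0.497 is correct, and the 35% shortfall does not arise. This is plausible and cannot be excluded. It does not remove the fault, because the label would then be wrong instead of the number.

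A second argument is that a SAP reader can trace the figure. That is partly true: the SAP's total agrees with the n = 18 row of Table C. But the SAP keeps the per-arm wording and gives no per-arm value, and its bracketed total can equally be read as restating the design. The protocol has no such addition.

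Third, nothing in the design depends on the figure. Section 9.2 rests the study size on feasibility, the power in Table 11 uses 27 or 36 staff per arm, and SD 1.0 is one of two illustrative values; the documents give no observed SD for site-level change. At SD 0.5, 9 sites would give 0.384, narrower than 0.497. All of this stands and limits the consequence. It does not make the sentence correct at the SD it states.

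Two limits of the material also apply. The precision figures (graphs) that accompany the tables were not available, so the statement that n = 9 is not shown covers the tables only. The staff analyses are detailed in a separate SAP that was also not available, so it cannot be settled which site-level interval will be reported.

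**Conclusion.** The concern holds. In protocol section 9.2 the label (9 sites per arm) and the half-width (0.497 at SD 1.0) do not belong together: 0.497 is the value for all 18 sites, and 9 sites give 0.769. If per arm is meant, precision is overstated and the half-width should be 1.55 times as wide. If pooled is meant, the number stands and the per-arm label is the error. SAP section 2.4.1.2 resolves this only in part.

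The absolute values rest on the plan's own SD of 1.0 and on the paired-t formula that reproduces its table; the ratio does not depend on the SD. The effect is confined to this precision statement. Sample size, the Table 11 power figures and the planned tests are unchanged. It should be corrected, but it does not threaten the trial's conclusions.

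**What to change.** Replace the site sentence in protocol section 9.2 and SAP section 2.4.1.2 with one that gives both cases, for example: *With 9 sites per arm, the half-width of the two-sided 95% confidence interval for the mean site-level change is 0.769 (SD 1.0) or 0.384 (SD 0.5); with all 18 sites pooled over both arms it is 0.497 or 0.249.* Add an n = 9 row (0.384 and 0.769) to protocol Table 12 and SAP Table C.

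This wording is right whichever interval was intended. It costs one sentence and one table row in each document, and no sample size, power figure or analysis changes.

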6.3. Measures to Minimize Bias: Randomization and Blinding

For drug distribution purposes, the study will be single-arm, open-label study where all patients who pass screening will be assigned to CAB LA + RPV LA regimen.

For the purposes of implementation science/strategy, this study will be a two-arm study and sites will be either randomized to the Enhanced or Standard implementation strategy.

Cluster randomization will be applied because:

- Evaluation of intervention will be implemented at site level.
- For logistical convenience, and to avoid any contamination that could occur if implementation science interventions were provided for some subjects and not others within each site

Cluster randomization will be used to randomize sites in each country to either arm-e or arm-s. To achieve balanced implementation strategies across the sites, randomization may be stratified by clinic features. This will ensure data can identify whether a certain implementation strategy performs differently within a country or not, as well as between different countries.

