Table 14 Sensitivity Analysis for Sample Size versus Half-Width (Precision)-Two-Sided 95% Confidence Interval (for Patients)

Figure 7 Sensitivity Analysis for Sample Size versus Half-Width (Mean Diff to Limit) versus Sample Size - Patients (Multiple Confidence Levels)

As explained in other parts of this protocol, launching CAB LA + RPV LA in the real world may present challenges that were not observed in a clinical trial setting. Therefore, in addition to the primary analyses which focuses on study staff participants data, statistical analyses of patient outcome endpoints will be performed to evaluate changes in study patients' satisfaction score results, to allow a formal comparison between the two implementation strategies.

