9.4. Statistical Analyses

There will be two main reporting and analysis timeframes. First, will be the primary complete analyses which will be conducted when the last study participant has completed their CAB LA + RPV LA study treatment up to Dose 7. All study staff participant (site-level) questionnaire and interview data, plus all study participant (subject-level) data will be included in this reporting and analysis effort.

Once all study participants have completed the study, final analyses of the data will also be conducted

The statistical analysis plans will be finalized prior to DBL and it will include a more technical and detailed description of the statistical analyses described in this section. This section is a summary of the planned statistical analyses of endpoints. Analysis on patient

study participant data will account for sites that patients are nested in. The reporting analysis plan will provide further details of the analyses.

As mentioned above, this study has both site- and subject-level outcomes and each outcome will be analyzed and summarized accordingly.

Qualitative interview data will be summarized by a third party and reported as part of the overall study results (CSR). Details of these analyses will be described in a separate analysis plan provided by the CRO partner under GSK's oversight.

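### The 0.131 half-width for 225 patients per arm holds only for a within-arm change with independent patients; no precision is given for the planned between-arm comparison or after allowing for site

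*Protocol*

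**What the plan says.** Protocol 9.2, under the patient population, describes the two-sided 95% interval expected from 225 patients in each arm by this half-width: "distance from the mean paired difference to the limits that is equal to 0.131 when the estimated standard deviation of the paired difference is 1". The calculation is repeated in Table 14 for 100 to 250 patients at SD 0.5 and 1.0. SAP 2.4.1.3 and its Table E carry the same text and figures.

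Four other places bear on what that figure can mean:

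- Protocol 6.3: "Cluster randomization will be used to randomize sites in each country to either arm-e or arm-s". The overview table in SAP 2.3 gives the site allocation as 1:1.
- Protocol 9.2, provider part: "An overall average number of 9 sites, per arm".
- Protocol 9.4: the analysis of patient "study participant data will account for sites that patients are nested in".
- The closing paragraph of protocol 9.2 says patient outcomes will be analysed "to allow a formal comparison between the two implementation strategies". The matching paragraph in SAP 2.4.1.3 calls that comparison informal, and SAP 2.1.1, which lists departures from the protocol's analysis, does not mention the change.

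Protocol 9.4.2 then plans to compare mean patient AIM, IAM and FIM scores between the arms and to report p-values. Neither document gives an ICC, a design effect, site-level degrees of freedom or a between-arm half-width for patients.

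**The concern.** The figure and the design do not match in two ways.

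First, the figure has no site term. Patients at one site share staff, clinic pathway and implementation support, so their change scores may be correlated, and the protocol itself commits the patient analysis to respecting that.

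Second, the figure is for change within one arm, whereas the section ends on a comparison of two arms. The difference between two independent means is less precise than either mean alone.

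A reader planning around Table 14 would expect the patient scores to resolve smaller differences between strategies than they can. When the between-arm interval comes out wider than 0.131 suggests, nothing in the plan tells the reader that this was to be expected.

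**Working it through.** **Inputs.** From protocol 9.2: 225 evaluable patients per arm, 95% two-sided, SD of the paired difference 1.0 (also 0.5), 9 sites per arm. Hence 225/9 = 25 patients per site, taken as equal. The ICC is not in the documents, so the values 0.01, 0.05 and 0.10 are assumptions, with 0 as the reference.

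**1. Reproduce the plan's figure.** One-sample paired t interval: half-width = t(0.975, n−1) × SD/√n.

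- SD 1.0: t(0.975, 224)/√225 = 1.971/15 = 0.131, as stated.
- SD 0.5: 0.066, as stated.

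All seven rows of Table 14 reproduce this way. The formula treats patients as independent and covers one arm only.

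**2. Between arms, no clustering.** Half-width = t(0.975, 448) × √(2/225) = 1.965 × 0.0943 = 0.185 at SD 1, or 0.093 at SD 0.5. That is 0.185/0.131 = 1.41 times the stated figure, and it needs no assumption about the ICC.

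**3. Allow for site.** Design effect DE = 1 + (25 − 1) × ICC. With sites treated as random:

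- within arm: t(0.975, 8) × √(DE/225), where 9 sites give 8 df and t = 2.306;
- between arms: t(0.975, 16) × √(2 × DE/225), where 18 sites give 16 df and t = 2.120.

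Results at SD 1, with values on patient-level df (224 or 448) in brackets so that the effect of the df can be told apart from that of the ICC:

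| Assumed ICC | DE | Effective patients per arm | Within arm | Between arms |
|---|---|---|---|---|
| 0 | 1.00 | 225 | 0.154 (0.131) | 0.200 (0.185) |
| 0.01 | 1.24 | 181 | 0.171 (0.146) | 0.223 (0.206) |
| 0.05 | 2.20 | 102 | 0.228 (0.195) | 0.296 (0.275) |
| 0.10 | 3.40 | 66 | 0.283 (0.242) | 0.369 (0.342) |

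Halve every half-width for SD 0.5.

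**4. Two refinements.**

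- Sites are randomised within five countries. Fitting country would leave 18 − 2 − 4 = 12 df, with t = 2.179. At the same standard error the between-arm values widen by 2.179/2.120, about 3%; any between-country variance removed would work the other way.
- Unequal site sizes widen the intervals. With an assumed coefficient of variation of 0.5 and ICC 0.05, DE = 1 + (1.25 × 25 − 1) × 0.05 = 2.51, giving 0.244 within arm and 0.317 between arms.

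**The case against.** The strongest reply is that the plan claims no more for 0.131 than it is. The text labels it per strategy group and as a paired difference, the number is correct, and Table 14 is presented as a sensitivity analysis over several sample sizes and two SDs. Protocol 9.2 also says that the study size comes from feasibility, and the patient scores are secondary. All of that stands. A reader might infer an arithmetic error, or that 450 patients is the wrong number; the documents support neither.

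A second reply concerns the within-arm figure. Protocol 9.4 names no model. At an ICC of 0 with patient-level df, 0.131 stands. If sites were fixed effects of equal size, the within-arm half-width would be about 1.971 × √((1 − ICC)/225), or 0.128 at an assumed ICC of 0.05, slightly better than stated. So the tempting claim that the planned analysis cannot reach 0.131 within an arm goes too far. Fixed site effects do not help the between-arm contrast, because each site belongs to one arm only.

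Third, survey analyses are deferred to a separate contractor's plan (SAP section 3), which is not among these documents and may specify the site model. It may, but no later model restores precision that site randomisation has cost, and Tables 14 and E stand in the documents at hand.

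Finally, a reader might infer that the trial's reported intervals will be too narrow. That does not follow: reported intervals will come from the data, and the protocol commits to allowing for site.

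**Conclusion.** The point holds as an overstated precision figure for a secondary endpoint. The 0.131 is correct for the mean change in one arm with independent patients, and the plan does not say that it is limited to that case. The planned between-arm comparison of patient scores has no stated precision. At SD 1 and 225 patients per arm its half-width is at least 0.185 for any ICC of 0 or more, and 0.200 on 16 site-level df. This part rests on no assumed ICC.

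The rest depends on assumptions that the documents do not supply: an ICC of 0.01 to 0.10, equal sites of 25, and sites treated as random. Under these, the half-width is 0.171 to 0.283 within arm and 0.223 to 0.369 between arms, the latter about 1.7 to 2.8 times 0.131. The documents do not present 0.131 as between-arm precision. The link is that the same section closes on that comparison and gives no other patient figure.

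**What to change.** In protocol 9.2 (Table 14) and SAP 2.4.1.3 (Table E):

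- Label 0.131 as per arm, within-arm change, unadjusted for site.
- Add between-arm and site-adjusted half-widths over an ICC range that is stated to be assumed, with the df given. For 9 sites of 25 per arm at SD 1, the entries are those tabulated in the working, from ICC 0 to 0.10, with sites random. Note that country strata would reduce the df slightly.
- Name the model that will allow for site, or point to the plan that does.
- Reconcile the formal comparison in the protocol with the informal one in the SAP. If informal is intended, record it in SAP 2.1.1 and revisit the p-values in protocol 9.4.2.

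The cost is a change of wording and one table. The stated precision becomes less favourable. No extra patients, visits or procedures are needed, and enrolment does not change.
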